#### 8.4 Analysis

- a) **Intention to treat**: All analyses will be performed on an "intention to treat" basis. That is, the average costs of patients in each arm will be determined retaining all patients in their originally randomized arm, irrespective of the treatment that is ultimately used for that patient. If a patient is lost to the trial by death, transplantation, withdrawal of consent, or move to a non-participating center, that patient will be included in his/her original randomization group, but the costs will be pro-rated for the actual time in the trial.
- b) **Sensitivity analysis**: An important component of any economic evaluation is an analysis of the uncertainty surrounding the differences in expected costs and expected utility of the alternative strategies. Our approach to the analysis of uncertainty will be informed by the guidelines of the Panel on Cost-Effectiveness in Health and Medicine (Gold et al, 1996):
  - Conduct univariate (one-way) sensitivity analysis for all variables to determine where uncertainty about some key parameters could have a substantial impact on the conclusions. A tornado diagram will be used to sort the variables by their magnitude of effect (sensitivity). The potential major sensitive parameters include rate of hospitalization, cost for a hospital stay, EPO dose and rate of EPO use, nursing time devoted to training and home support, proportion of home nocturnal to all dialysis patients, and various techniques to allocate overhead to each modality. For the lifetime analysis, additional sensitive parameters include technique survival (length of time on randomized modality), patient survival, and discount rate.
  - Conduct multivariate (2- or 3-way) sensitivity analysis for important parameters. This explores potential magnitude of effect when two or more key parameters are altered together. The results from univariate sensitivity analysis will serve as a guide to select the variables in multivariate sensitivity analysis. The potential sensitive parameters pairs may include hospital costs and rate of hospitalizations, or EPO dose and rate of EPO use.
  - Construct a confidence or credible interval around the cost-effectiveness result. Bootstrap simulation with replacement will be utilized to derive costs and

utilities and associated incremental cost effectiveness ratio (ICERs) with 95% confidence intervals. Acceptability Curves will be constructed to determine the probability of nocturnal hemodialysis being cost-effective over the standard hemodialysis under certain cost-effectiveness thresholds. Conventionally, ICERs of less than \$50,000 per QALY are considered very cost-effective whilst those with an ICER of between \$50,000 and \$100,000 per QALY are considered moderately cost-effective

In addition, the estimates from physician reported utilizations will be incorporated for sensitivity analysis.

- c) **Time-frame for analysis**: The economic evaluation will consider two time-frames: a) within trial one-year period, and b) the lifetime of the patient. We recognize specifically that the costs of the non-dialysis component of care may decline over the year of observation, such that the average over the year might underestimate the long-term impact on costs (and benefits). This will be assessed by estimating total costs within the first and the final four months of the study. We shall use a probabilistic economic model to project long-term survival, health benefits, and costs beyond the study period and extend the findings to patients and facilities not included in the trial. Lifetime costs and benefits will be **discounted at a rate of 3%**.
- d) Objective 1 Costs of dialysis: Costs per month of dialysis for patients in the two study arms will be determined by summing the per dialysis costs of dialysis as listed in Table 10 - 11 above and multiplying this sum by the average number of outpatient dialysis sessions per month for the patients in each arm of the study. This analysis may be useful to CMS and other payers in setting appropriate payment rates for nocturnal hemodialysis.
- e) **Objective 2 Total CMS covered costs**: Costs per month of CMS covered care will be summed by summing the average per month costs of dialysis (as in (d) above) and of other covered care as in Table 13 above.
- f) Objective 3 Cost-Effectiveness: The impact of randomization to nocturnal hemodialysis (compared with standard 3 times weekly home hemodialysis) on life expectancy will be determined directly from survival of patients in the two arms of this trial. Utility (quality of life) will be determined from the Health Utilities Index. The impact of assigned treatment on quality adjusted life years will be calculated from the measures. If as hypothesized, nocturnal hemodialysis is a "dominant" strategy, improving survival/health utility and lowering costs, differences in survival, utility, dialysis costs, and total CMS costs will be presented in a cost-consequences framework. If, conversely, survival/health utility is improved, but total CMS costs are increased, we will calculate the incremental cost-effectiveness ratio (cost per qualityadjusted-life-year), to permit comparison with other possible ways for CMS to spend its health care dollar.
- g) **Objective 4 Comparison of nocturnal with short daily hemodialysis:** While not a primary purpose of this randomized trial, there will be interest in comparing the outcomes of overnight nightly home hemodialysis with the outcomes of short daily incenter dialysis being studied in the companion trial performed by this consortium. These results will not be directly comparable as the patient groups from which patients will be randomized are different. However the degree of difference (or conversely, of

comparability) may be estimated by comparison of the outcomes in the standard arm (conventional home hemodialysis three times weekly) in this trial and in the companion trial. We shall make such comparisons.

- h) Power: We acknowledge that the power for some of the above proposed analyses is likely to be poor. Specifically, formal power analyses have suggested that there will be low power to detect differences in patient survival and the rate of hospitalizations. The latter will likely be a major component of the total CMS costs of management of a dialysis patient. Therefore a major focus of this economic analysis will be the sensitivity analysis to determine robustness of our analyses.
- i) **Objective 5 Economic and social impact of nocturnal hemodialysis on the patient, his/her family, and society:** Information on these aspects of the economic impact of nocturnal hemodialysis is likely to be considerably more subjective and less quantitative than for the above components of the economic analysis. We shall therefore make no attempt to merge these data with the economic analyses above, but will rather simply list the conclusions together with the other information in the costconsequences framework.

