## 3.2 Duration of Treatment and Follow-up

Each patient will be treated in his/her respective group for 12 months, or until death, recovery of renal function or a stop-point is met (transplant, change to peritoneal dialysis, relocation to a nonstudy center – see Section 7.3). Except for those subjects who are transplanted, change to peritoneal dialysis, or die, data collection and follow-up will continue for all patients for a minimum of 12 months. For patients who relocate to a non-study dialysis unit or transfer to home hemodialysis during their 12 months of follow-up, all attempts will be made to collect vital status, the two coprimary outcomes (see Section 3.1), and the centrally administered quality of life questionnaires. When possible, the complete data collection procedures designated in the protocol will be maintained for subjects who switch to in-center HD. Those patients who are transplanted or switch to peritoneal dialysis will no longer be followed. Otherwise, no matter what happens to a patient, it is recommended that all attempts be made to encourage any subject who misses the two co-primary outcomes to provide these data for up to six months past his or her F12 window. Patients who need to switch from home HD to in-center HD due to an acute complication, new comorbid medical condition(s), patient or partner burnout or patient desire will continue to be followed in his/her respective group. Re-evaluation of each of these patients will be performed at regular intervals to determine if the patient is able and willing to restart home HD therapy. Adverse events hospitalizations and serious adverse events should be recorded for an additional 30 days after the patients' F12 month ends. Starting with the first dialysis session held at least 30 days after the patients' F12 month ends, one week of data should be recorded from the dialysis unit's run sheets. This data will include start time, end time, and pre and post weight and blood pressure for each dialysis session held during the week.

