#### 7.4 Losses to Follow-up

Efforts will be made to follow all randomized subjects for 12 months, irrespective of their adherence to the randomized therapy. However, certain situations may preclude complete data collection for the full 12 months (losses to follow-up).

The randomized therapy and routine data collection will be discontinued in the following situations:

- a. Subject withdraws consent for data collection
- b. Subject changes to peritoneal dialysis
- c. Subject receives renal transplant
- d. Subject relocates to a non-study center.

For patients who are lost to routine data collection for reasons b - d above, all attempts will be made to collect vital status. For patients who relocate to a non-study dialysis unit or transfer during their 12 months of follow-up, all attempts will be made to collect vital status, the two co-primary outcomes, and the centrally administered quality of life questionnaires.

All losses to follow-up with reason will be reported to the DCC (discontinuation of therapy form). The Adherence Committee will review all losses to follow-up on a monthly basis.

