### 8.2 Purpose

If nocturnal home hemodialysis proves to be effective in improving health outcomes, it will be important to understand:

- a) The changes in dialysis center costs to provide this mode of hemodialysis,
- b) The changes in overall health care costs to insurers (principally CMS) of patients using this mode of hemodialysis,
- c) The cost-effectiveness of the intervention (change in insurer costs per change in quality adjusted life-years)
- d) Costs per month for in-center hemodialysis (three times per week) obtained from the Daily Trial will be used to compare the monthly costs of nocturnal home hemodialysis with 3 times per week in-center hemodialysis.

The purpose of the economic analysis in this trial is to provide answers to these questions.

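### In the economic analysis, one undefined pro-rating rule covers both deaths and patients who leave alive, and omits peritoneal dialysis switchers, so the one-year cost and cost per QALY are not soundly defined

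*Protocol*

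**What the plan says.** Section 8.4a keeps every patient in the randomized arm for costing, "irrespective of the treatment that is ultimately used for that patient". It then sets one rule for patients lost by any of four exits, namely death, a transplant, withdrawn consent or relocation outside the study centers. For all of them alike, "that patient will be included in his/her original randomization group, but the costs will be pro-rated for the actual time in the trial". The protocol does not say what pro-rating means arithmetically.

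Change to peritoneal dialysis is not among the four exits. Section 7.4 nevertheless lists "Subject changes to peritoneal dialysis" under the heading sentence "The randomized therapy and routine data collection will be discontinued in the following situations", after which vital status is still to be sought. Section 3.2 goes further: "Those patients who are transplanted or switch to peritoneal dialysis will no longer be followed".

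The quantity at stake is set in Section 8.2c as "change in insurer costs per change in quality adjusted life-years". Section 8.4c gives it a one-year within-trial frame and a lifetime frame. On the benefit side, Section 8.4f says that "life expectancy will be determined directly from survival of patients in the two arms of this trial", with utility from the Health Utilities Index. Objectives 1 and 2 (Sections 8.4d and 8.4e) are instead expressed as cost per month.

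**The concern.** A patient who dies in month 5 has a fully known one-year cost: what was spent to month 5, and zero after. A patient transplanted in month 5 goes on consuming care that the trial no longer records. The first is a complete observation and the second is censored. A single time adjustment cannot be correct for both when the target is cost over one year.

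The mismatch carries into the cost-effectiveness ratio. If a death is scaled up to a full year, the arm is charged for months that Section 8.4f credits to nobody. If only accrued cost is counted, survival can continue in the denominator after the cost record has stopped, because Section 7.4 still seeks vital status after transplantation, peritoneal dialysis and relocation.

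The protocol separates the two kinds of exit elsewhere. Section 9.3 ranks deaths as outcomes and censors transplants. Section 9.6 models death as an event and censors at transplantation and transfer, because hospitalizations are not recorded after those points. Section 8.4h expects hospitalization to be a major part of total cost, yet Section 8.4a does not carry the distinction over.

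Section 8.1 hypothesizes dominance, meaning better outcomes at lower cost. That conclusion turns on the sign of the cost difference, so an error of a few per cent can matter if the true difference is small. The parameter sensitivity analyses and bootstrap of Section 8.4b do not repair it: they vary inputs, or resample whatever costs the rule has produced. The pattern-mixture analysis of Section 9.9 is not tied to costs.

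**Working it through.** The protocol gives no figure for this effect, so there is none to reproduce. The following illustrates its size.

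**Inputs from Section 9.11.** Control mortality is 7%/yr. A 20% reduction gives 0.8 × 7% = 5.6%/yr in the nocturnal arm. Transplantation is 6%/yr in both arms. Exit times are exponential.

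**Assumptions, not in the protocol.** Cost per month is constant. Patients who leave alive go on costing the same. Other exits alive (peritoneal dialysis, relocation, withdrawal) run from 0 to 10%/yr, since no rate is stated.

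**Formula.** With total exit rate r, mean observed time in one year is (1 − e^−r)/r. The reference value uses deaths only, because cost truly stops at death and continues after an exit alive. Results are fractions of a full-year cost, with the error relative to the reference.

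| Quantity | Control | Nocturnal |
|---|---|---|
| Reference (deaths only) | (1 − e^−0.07)/0.07 = 0.9658 | (1 − e^−0.056)/0.056 = 0.9725 |
| Accrued cost only, transplantation 6% | (1 − e^−0.13)/0.13 = 0.9377 (−2.9%) | (1 − e^−0.116)/0.116 = 0.9442 (−2.9%) |
| Accrued cost only, plus 10% other exits alive | (1 − e^−0.23)/0.23 = 0.8933 (−7.5%) | (1 − e^−0.216)/0.216 = 0.8994 (−7.5%) |
| Scaled to a full year, or person-time annualized | 1.0000 (+3.5%) | 1.0000 (+2.8%) |

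Counting accrued cost is right for deaths and wrong for exits alive. Scaling up is tolerable for exits alive that are unrelated to cost, and wrong for deaths.

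**Between arms.** The reference nocturnal/control ratio is 0.9725/0.9658 = 1.007.

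- Accrued cost, transplantation only in both arms: 0.9442/0.9377 = 1.007, so the error cancels.
- Accrued cost, other exits alive 2% control and 10% nocturnal: (1 − e^−0.15)/0.15 = 0.9286 for control, and 0.8994/0.9286 = 0.9685. The error is 0.9685/1.007 − 1 = −3.8%.
- The same rates reversed: (1 − e^−0.136)/0.136 = 0.9350 for nocturnal, and 0.9350/0.8933 = 1.047. The error is +3.9%.
- Scaled to a full year: 1.000/1.007 − 1 = −0.7%.

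**Peritoneal dialysis.** Here the check is textual. Section 8.4a promises costs whatever treatment is finally used, Sections 3.2 and 7.4 stop the routine data that would supply them, and the list in 8.4a does not name this exit. Section 5.3d tracks change to peritoneal dialysis as a sign of burn-out on nocturnal treatment, so a difference between arms is plausible, but no rate is given.

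**The case against.** The strongest reply is that pro-rating for time in the trial naturally means cost per unit of observed time. Objectives 1 and 2 are costs per month, and with a person-time denominator the months after an exit simply do not enter. This stands, and those two objectives are little affected. It does not rescue Objective 3: turning a monthly cost into a one-year cost without allowing for death gives the 3.5% and 2.8% overstatements above.

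Three stronger inferences are tempting and are not supported.

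- A reader might conclude that peritoneal dialysis switchers are entered at zero cost after the switch. No passage says so. Section 7.4 classes them as losses to follow-up, and extending the 8.4a rule to them is an ordinary reading. What is established is a gap in the list.
- A reader might conclude that all resource data stop at exit. Table 10 rests largely on expert judgment, personnel records, price lists and cost reports, and the claims of Medicare-primary patients need not stop. Dependence on trial forms is real for medications, and dependence on trial-recorded stays is real for Canadian and HMO patients.
- A reader might subtract 7% deaths from the 20% without 12-month data and treat the rest as exits alive. The 80% in Section 9.11 is the rate of PHC and LV mass measurement; a patient who misses a scan can still supply costs. Transplantation is the only exit alive with a stated rate.

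It is also fair that the choice of estimator usually belongs in an analysis plan, and that Section 8.4h concedes poor power and makes sensitivity analysis a major focus. But the protocol does not leave this open: it states a rule, and the rule joins two things that need different handling.

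**Conclusion.** The point holds for the one-year cost and the cost per QALY of Objective 3. Under either reading of the rule each arm's one-year mean is off by a few per cent: about 2.9% too low from transplantation alone, up to about 7.5% too low with assumed further exits, or 3.5% and 2.8% too high if scaled up. These sizes rest on constant monthly cost and on leavers costing the same as those who stay.

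A reader might infer that the comparison between arms is biased, perhaps in favor of nocturnal dialysis. The protocol does not support that. With similar exit patterns the between-arm error is small; about 4% needs an assumed 2% versus 10% split in exits alive, and the sign follows whichever arm loses more patients. The co-primary and main secondary outcomes are untouched. This is a minor but worthwhile correction.

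**What to change.** In Section 8.4a:

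- Add change to peritoneal dialysis to the list of exits.
- State that pro-rating for Objectives 1 and 2 means cost per month of observed time.
- For the one-year cost and QALY analysis, count a death at its actual cost with zero afterwards, over the same 12 months as the QALYs.
- Treat every exit alive (transplantation, peritoneal dialysis, consent withdrawal, relocation) as censored on the date that resource data stop.
- Estimate the arm mean with a censoring-adjusted method, either monthly cost weighted by the Kaplan-Meier probability of survival or inverse-probability-of-censoring weights, and run it inside the bootstrap already planned.
- Add a sensitivity analysis by reason for exit, since burn-out exits may be related to cost.

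This takes a few lines of text and a standard estimator on data already collected. The price is somewhat wider cost intervals and reliance on the assumption that those who leave alive would have cost about the same as comparable patients who stay. With about 45 patients per arm that assumption cannot be tested well, which is why the sensitivity analysis is needed.

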## 8. Economic Evaluation

### 8.1 Hypothesis

We hypothesize that savings in non-dialysis health care costs due to better health from nocturnal home hemodialysis will offset its additional dialysis related expenses. That is, we hypothesize that nocturnal home hemodialysis will be a "Dominant Strategy" (better outcomes with reduced costs).

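### The planned bootstrap 95% interval for the ICER carries no quadrant condition, so it does not order replicates by cost-effectiveness; an interval for net monetary benefit would

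*Protocol*

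**What the plan says.** All of this is in Section 8 of the protocol. Section 8.1 expects better outcomes at lower cost: "We hypothesize that savings in non-dialysis health care costs due to better health from nocturnal home hemodialysis will offset its additional dialysis related expenses".

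Section 8.4(b) lists one-way sensitivity analyses with a tornado diagram, then two- and three-way analyses, then a bootstrap: "Bootstrap simulation with replacement will be utilized to derive costs and" "utilities and associated incremental cost effectiveness ratio (ICERs) with 95% confidence intervals". The next sentence adds a further summary: "Acceptability Curves will be constructed to determine the probability of nocturnal hemodialysis being cost-effective over the standard hemodialysis" at given thresholds. The reading convention follows: "Conventionally, ICERs of less than \$50,000 per QALY are considered very cost-effective", with a moderate band from $50,000 to $100,000.

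Section 8.4(f) treats the outcomes separately. If nocturnal dialysis is dominant, the differences in survival, utility, dialysis costs and "total CMS costs will be presented in a cost-consequences framework". The other branch reads: "If, conversely, survival/health utility is improved, but total CMS costs are increased, we will calculate the incremental cost-effectiveness ratio". No branch covers worse survival or utility.

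Section 8.4(h) concedes that power for some of these analyses is likely to be poor and makes the sensitivity analysis a major focus. Section 2.2 sets 90 patients with equal allocation, so 45 per arm.

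**The concern.** An ICER is a cost difference divided by a QALY difference, and its sign does not say which therapy is preferable. A negative value can mean the best result (cheaper and better) or the worst (dearer and worse). A positive value can mean dearer and better, or cheaper and worse, and a low figure is good in the first case and bad in the second.

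Section 8.4(f) deals with this for the point estimate. The interval in 8.4(b) carries no such condition, and bootstrap replicates can fall in any quadrant whatever the point estimate is. Sorting their ratios and cutting at 2.5% and 97.5% puts dominated replicates next to dominant ones at the low end.

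The protocol's own expectation makes this relevant. It hypothesizes dominance, where the ratio is negative and ambiguous, and it anticipates imprecise estimates. At stake is whether the published interval means anything to a payer, since 8.4(f) intends the ratio to support comparison with other uses of CMS money.

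**Working it through.** The protocol states no interval, SD or sample-size figure for the economic analysis, so there is nothing of its own to reproduce. The check has three parts.

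**1. Sign of the ratio.** Write dC for the cost difference and dE for the QALY difference (nocturnal minus conventional). ICER = dC/dE. Net monetary benefit at $50,000 per QALY is NMB = 50,000 × dE − dC.

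| Quadrant | dC | dE | ICER | NMB |
|---|---|---|---|---|
| Cheaper, better (dominant) | −$5,000 | +0.05 | −$100,000 | 2,500 + 5,000 = +$7,500 |
| Dearer, worse (dominated) | +$5,000 | −0.05 | −$100,000 | −2,500 − 5,000 = −$7,500 |
| Dearer, better | +$5,000 | +0.05 | +$100,000 | 2,500 − 5,000 = −$2,500 |
| Cheaper, worse | −$5,000 | −0.05 | +$100,000 | −2,500 + 5,000 = +$2,500 |

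Four results of different merit give two ICER values. Net benefit separates all four. This part needs no assumption about SDs.

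**2. Whether replicates would spread over quadrants.** Assumed, because the protocol gives no values: one-year QALY SD 0.15 to 0.25 and annual cost SD $20,000 to $40,000. With 45 per arm, the standard error of a difference is SD × √(2/45) = SD × 0.211.

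- QALYs: 0.15 × 0.211 = 0.032, and 0.25 × 0.211 = 0.053.
- Costs: $20,000 × 0.211 ≈ $4,200, and $40,000 × 0.211 ≈ $8,400.

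For a trial whose estimate equals a true gain of 0.05 QALY, the share of replicates showing a QALY loss is about Φ(−0.05/0.032) ≈ 6% at the smaller SD and Φ(−0.05/0.053) ≈ 17% at the larger.

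**3. Simulation of the case in which 8.4(f) reports an ICER.** Settings: 45 per arm, 600 trials per setting, 1,000 bootstrap resamples each, normal QALYs, gamma costs with an assumed control mean of $70,000, a true gain of 0.05 QALY and a true cost excess of $5,000 or $10,000. Only trials with a better-and-dearer point estimate were kept.

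- On average roughly 7–15% of replicates were dominated (one repeat gave 8–16%). Their ratios are negative, so they sort at the favourable end.
- The lower 95% limit was negative in 76–98% of these trials. Dominant and dominated replicates both contribute to that tail, and the interval cannot tell them apart.

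**Illustration with worse health.** With a true loss of 0.05 QALY, +$10,000, QALY SD 0.15 and cost SD $20,000, 20,000 resamples gave a percentile ICER interval of −$1,708,449 to +$918,231. A plain count of replicates with ICER below $50,000 gave 0.947. The share with positive net benefit at $50,000 was 0.003.

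**The case against.** Four points can be made for the plan.

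**The interval is one item among several.** A reader might infer that the treatment of uncertainty rests on the ICER interval. It does not: one-way and multi-way analyses and acceptability curves are planned as well. A 95% net-benefit interval lying above zero at $50,000 is the same event as an acceptability curve above 97.5% there, so a curve built on net benefit already carries much of what is proposed. This stands. The protocol does not, however, say how the curve is computed. A curve that counts ratios below the threshold, which is the only convention written down, repeats the sign error.

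**Section 8.4(f) gates the ICER.** This stands for the point estimate and disposes of the most alarming reading. If the interval is read in every trial regardless of quadrant, simulations under the assumed SDs put it wholly below $50,000 in 24–81% of trials when the truth is −0.10 QALY and +$10,000, and in 7–28% when it is −0.05 QALY (up to 34% in repeats). Restricted to trials with a better-and-dearer point estimate, the count was 0 of 600 in every setting. The gate does not reach the replicates, which is the part that remains.

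**No decision rule is attached to the interval.** The protocol does not declare cost-effectiveness when the upper limit is below $50,000; it cites a convention for ICERs. It also does not name the percentile method, although sorting bootstrap ratios is the plain reading. This too argues against quoting error rates, but not against the interval being uninterpretable.

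**The sizes depend on assumed inputs.** They do. The sign result does not.

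**Conclusion.** The point holds as a defect in a stated method. Section 8.4(b) fixes a 95% interval for a ratio that does not rank replicates by merit once they spread over quadrants. It does not carry over the restriction in 8.4(f), and 8.4(f) is silent on worse health.

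Under the assumed SDs and a true gain of 0.05 QALY, about 7–15% of replicates are dominated yet sorted as favourable in the one case where 8.4(f) reports an ICER, and the lower limit is usually negative.

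Two stronger readings are not supported. The 24–81% and 7–28% figures are not the plan's error rates, because they ignore the 8.4(f) restriction and impose a rule that the protocol does not state. Nor should a power loss be claimed. Under true dominance (+0.10 QALY, −$10,000) the ICER interval falls below $50,000 in 5 to 39 percentage points fewer trials than net benefit favours, but 8.4(f) sends a dominant result to a cost-consequences display, not to an ICER.

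The matter is minor. It concerns the secondary economic objective and leaves the co-primary outcomes untouched.

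**What to change.** Amend Sections 8.4(b) and 8.4(f) as follows, using the same bootstrap replicates:

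- Replace the ICER interval with 95% intervals for incremental cost, incremental QALYs and incremental net monetary benefit at $50,000 and $100,000 per QALY, reported in every quadrant.
- Define the acceptability curve as the share of replicates with positive net benefit at each threshold.
- Give the ICER as a point value only when both the QALY and the cost difference are positive.
- Add the missing branch to 8.4(f): when survival or utility is worse, report the two differences and net benefit, with no ICER.

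The cost is a few sentences of wording, with no new data and no extra resampling. The one loss is that the report will no longer quote a single ratio with an interval, which some readers expect.
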